Appendix 5: Recognition of Adverse Events

Management of Adverse Events

Definitions

Adverse Event (AE): any untoward medical occurrence in a clinical trial subject administered a pharmaceutical product, not necessarily related to the study drugs or TB drugs. FILL IN ADVERSE EVENTS REPOTING FORM and record on patient's weekly data collection form and medical file. Report to [name] and [name] [name] as per Safety Reporting Flwoshart.

Serious adverse event (SAE): any untoward medical occurrence in a clinical trial subject administered a pharmaceutical product, which is life-threatening, results in death, requires hospitalisation or prolongation of existing hospitalisation, results in significant disability / incapacity or congenital anomaly / birth defect. FILL IN SERIOUS ADVERSE EVENTS REPOTING FORM and record on patient's weekly data collection form and medical file. Report to [name] and [name] [name] as per Safety Reporting Flwoshart.

Potential study drug-related AE

Arginine

- Diarrhoea
- Bloating
- Nausea
- Vomiting
- Mild to moderate abdominal pain
- Urticarial skin rash

Vitamin D

- Asymptomatic hypercalcaemia defined as $iCa^{2+} > 1.32 \text{ mmol/L}$
- Symptomatic hypercalcaemia i.e. $iCa^{2+} > 1.32$ mmol/L with one or more of the following symptoms or signs:
 - o Gastrointestinal: Nausea, Vomiting, Abdominal pain, Constipation, Anorexia
 - Neurological / Psychiatric: Fatigue, Irritability, Confusion, somnolence, Coma
 - Renal: Polyuria, dehydration
 - Others: Bone pain, itch.

Syndromic management of adverse events adapted from (1)

Side effect	Study drug most likely to be	TB drug most likely to be	Perform liver function	Perform serum ionised	Management		
	responsible	responsible	tests	calcium			
					Hypercalcaemia	Abnormal LFTs identified	No biochem. abnormality
Minor							
Mild to moderate anorexia, nausea, abdominal pain, bloating	Either L-arginine or vitamin D	Rifampicin > isoniazid	Yes	Yes	Withdraw patient from study, manage hypercalcaemia in standard fashion ¹	Follow standard protocol (monitor closely; consider H and R cessation if LFT elevation >5x normal)	Advise taking medications with meals
Mild to moderate diarrhoea	arginine	Rifampicin > isoniazid	Yes	No		As above	No change required unless diarrhoea is severe and persistent
Constipation	vitamin D	none	No	Yes			Standard treatment
Joint pains	neither	pyrazinamide	No	No	Give aspirin or NSAID		
Burning sensation in feet	neither	isoniazid	No	No	Give pyridoxine 50-75mg daily		
Flu-like symptoms	neither	rifampicin	No	No	Aspirin, continuation of rifampicin		
Orange / red urine	neither	rifampicin	No	No	reassurance		
Major							
Severe Anorexia, nausea, abdominal pain	vitamin D > arginine	Rifampicin > isoniazid	Yes	Yes	Withdraw patient from study, manage hypercalcaemia in standard fashion ¹	Cease R &/or H and follow usual procedure	Cease arginine and follow steps below ²
Severe diarrhoea	arginine	Rifampicin > isoniazid	Yes	No		Follow standard protocol (monitor closely; consider H and R cessation if LFT elevation >5x normal)	
Polyuria, dehydration	Vitamin D	none	No	Yes	Withdraw patient from study, manage hypercalcaemia in standard fashion ¹		
Non urticarial skin rash	neither	Most TB drugs	No	No	Stop all TB drugs. When rash resolved, restart in following order: H, R, Z, E, S S being used i.e. MDRTB)		
Urticarial skin rash	neither	streptomycin	No	No	Stop all TB drugs. When rash resolved, restart in following order: H, R, Z, E, S S being used i.e. MDRTB)		
Jaundice	neither	Most TB drugs	Yes	No		Stop TB drugs, reintroduce as per standard protocol	
Irritability, confusion, drowsiness, coma	Vitamin D	Most TB drugs	Yes	Yes	Withdraw patient from study, manage hypercalcaemia in standard fashion ¹	Stop TB drugs, reintroduce as per standard protocol	
Visual impairment	neither	ethambutol	No	No	Stop ethambutol and do not reintroduce		
Shock, purpura	neither	rifampicin	Yes	No	Stop rifampicin		

¹Treatment of hypercalcaemia this will not be a cause for automatic unblinding. Management will be will comprise oral hydration or intravenous hydration with normal saline, and / or oral prednisolone 15-60mg steroids, depending on severity, as per Adverse Events documents (2).

[figure not shown]
²Management of mild to moderate gastrointestinal upset attributed to arginine: this will not be a cause for unblinding. Study subject should be advised to take medications with food.

³Management of severe gastrointestinal upset attributed to arginine: this will not be a cause for unblinding. Study subject should be advised to take medications with food and halve the dose of the study drug for 1 week. If symptoms resolved, resume standard study drug dose and reassess. If intolerable symptoms continue at half dose, cease study drugs and reassess.

References

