3.3 Interventions

3.3.1 Informed consent

All patients will receive a detailed explanation regarding the reason for the study and what it involves, and regarding the voluntary nature of involvement in the study. Each eligible patient will be provided with verbal and written information in Bahasa Indonesia, or verbally using a Papuan translator if required.

Only patients who understand the study and provide informed consent will be enrolled. It will be explicitly stated that involvement is voluntary, participants are able to say no, and if they do initially consent, they can leave the study at any time they wish without prejudicing their treatment in any way. On withdrawing from the study, the researchers will provide ongoing positive encouragement and support for the participants to continue her/his TB treatment as usual, according to the National TB Protocol.

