3.3.3.4 Cessation of Study Medications

If medications are thought to be causing unacceptable symptoms, the treating doctor will determine the likely pharmacological cause (either of the two study drugs, or any of the four TB drugs) according to the strategy outlined in Appendix 5. If symptoms are determined to be due to arginine, this will be immediately ceased, and reintroduced at a lower dose as outlined in Appendix 5. If symptoms are due to vitamin D/hypercalcaemia, appropriate hypercalcaemia management will be instituted and any further scheduled dose of vitamin D will be cancelled. Any such events will be recorded on the 'Adverse drug events' sheet (Appendix 6) and notified immediately to the study investigators.

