3.3.5 Follow up

Usual follow-up according to the NTP includes monthly weight, repeat chest x ray and sputum at 2 and 6 months, and recording of symptoms, adherence and side-effects. Study participants in addition will receive evaluations as indicated in the table below. Default tracing will comprise three attempts to trace participants who miss two consecutive scheduled clinic appointments, which is standard practice in Timika.

test		week of TB treatment											
	0	1	2	3	4	5	6	7	8	12	16	20	24
weight (weekly)													
symptoms (weekly)													
sputum microscopy*													
sputum culture													
Chest Xray (routine 0,2,6 mths)													
expired NO													
spirometry													
6 minute walk test													
Respiratory Questionaire (SGRQ)													
blood													
HIV													
25(OH)D3 1,25(OH)2D3 & L-arginine													
iSTAT (including iCa2+, Hb)													
T cell CD3 ζ and function													

Notes:

1. Grey cells indicate that the test will be performed during this week (week 0 = diagnosis, other weeks are follow-up during TB treatment).

2. Routine tests/data collection as part of normal clinical practice in Timika TB clinic/RSMM: weight, symptoms, sputum microscopy (at week 0,8 and 24), chest Xray, HIV

3. Study-related tests/data collection: sputum microscopy (at week 1-7), sputum culture, expired NO, spirometry, 6 minute walk test, respiratory questionnaire and blood tests (vit D, arginine, Ca++ and T-cell function).

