5.2 Outcome Analysis

The primary analysis of all outcomes will be by intention to treat. All participants in the study will contribute outcomes for analysis whenever possible. Each participant's success or failure for the primary outcome will be determined by an independent observer who will be blinded to the intervention. Analyses will use Intercooled Stata 9.2 (Stata Corp, College Station, Texas, USA). 95% confidence intervals and/or p values <0.05 will be employed to signify statistical significance.

As per recent clinical journal requirements, ADAPT will be registered with the protocol registration system at Clinicaltrials.gov.

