6 ASSESSMENT OF SAFETY

6.1 Intervention Procedure

Potential adverse effects of L-arginine and vitamin D will be carefully monitored. Adverse effects from oral L-arginine are uncommon.(27) Use of up to 21g daily was not associated with adverse events in two studies(28, 74). Oral L-arginine 7g three times daily for 4 weeks was associated with diarrhoea in 3 of 27 patients, but this resolved on dose reduction to 7g twice daily(75). Minor gastrointestinal discomfort has been reported in up to 3% of patients(27, 76). We do not expect that this will be a problem but will monitor our study patients carefully for this adverse effect and treat accordingly.

Although much less common than in other granulomatous diseases, vitamin D supplementation in TB has the potential for hypercalcaemia from extra-renal $1,25(OH)_2D_3$ production(77). Based on our previous experience with vitamin D supplementation ([name], personal communication), and extensive review of the literature(60, 78-81), the risk of symptomatic hypercalcaemia as a complication of vitamin D supplementation at the dose proposed in this study(63) in patients with pulmonary TB is anticipated to be very low. Ionised calcium will be measured, using portable i-STAT cartridges in Timika, at 0, 2, 4 and 8 weeks. In the unlikely event of hypercalcaemia developing, the literature indicates that the most likely time of onset would be 2-4 weeks post commencement of anti-TB therapy. Patients found to have elevated *i*Ca²⁺ on follow up will have their Vit D/placebo dose withheld.

6.2 **TB Medication side effects**

All patients with pulmonary TB in the study will be treated with anti-tuberculous agents according to the standard NTP protocol. This comprises daily weight-adjusted doses of Rifampicin (R), Isoniazid (H), Pyrazinamide (Z) and Ethambutol (E). Medications are taken under direct observation by health care workers during the intensive phase. Treating doctors will comply with NTP guidelines with regards to standard monitoring for TB drug side effects.

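### Symptomatic hypercalcaemia stops vitamin D/placebo in 3.3.3.4 and 6.1 but ends study participation in Appendix 5; the baseline calcium rule also conflicts

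*Protocol*

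**What the plan says.** **On treatment.** Protocol 3.3.3.4 has the treating doctor identify the likely cause of unacceptable symptoms "according to the strategy outlined in Appendix 5". Where vitamin D or hypercalcaemia is the cause, "appropriate hypercalcaemia management will be instituted and any further scheduled dose of vitamin D will be cancelled". Section 6.1 treats any raised ionised calcium the same way: these patients "on follow up will have their Vit D/placebo dose withheld". Neither section takes the participant out of the study.

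The hypercalcaemia column of the Appendix 5 table says "Withdraw patient from study, manage hypercalcaemia in standard fashion" in four rows:
- mild to moderate gastrointestinal symptoms (classed as minor)
- severe gastrointestinal symptoms
- polyuria or dehydration
- irritability, confusion, drowsiness or coma

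**At baseline.** Ionised calcium above 1.32 mmol/L makes a patient ineligible in 3.2.2, in item 14 of the Appendix 1 form and in Appendix 6. In contrast, 3.3.2 has staff record whether the exclusion applied to the vitamin D/placebo component. Step 8 of the Appendix 15 blood instructions, at the same threshold, only takes vitamin D/placebo out of the drug pack. Step 2 of those instructions covers the baseline draw as well as follow-up.

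**Analysis.** Section 5.2 plans intention to treat and adds: "All participants in the study will contribute outcomes for analysis whenever possible".

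**The concern.** A doctor faced with nausea and a calcium of 1.35 mmol/L gets two instructions: stop one study drug, or end the patient's participation. The second would remove people because of a suspected effect of vitamin D, so losses could fall more heavily on one side of the vitamin D comparison.

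The only text on what follows withdrawal is in 3.3.1: "On withdrawing from the study, the researchers will provide ongoing positive encouragement and support for the participants to continue her/his TB treatment". It does not mention outcome visits. Note 3 to the follow-up table in 3.3.5 shows what is at risk: "Study-related tests/data collection: sputum microscopy (at week 1-7), sputum culture, expired NO, spirometry". Culture at 1 month is one primary outcome, and FEV1 is part of the 2-month composite. Section 6.1 says that "the most likely time of onset would be 2-4 weeks post commencement of anti-TB therapy", which is before the composite and partly before the culture. Later scheduled calcium checks, needed for the safety outcome, would also be at risk.

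The baseline conflict is of a different kind. Calcium is read before dosing and under blinding, so no bias arises. What is unclear is whether a hypercalcaemic patient is ineligible or may be enrolled on arginine/placebo alone, and so who counts as randomised.

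**Working it through.** **1. The texts side by side**

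| Situation | One instruction | The other instruction |
|---|---|---|
| Symptoms due to hypercalcaemia on treatment | 3.3.3.4: manage, cancel further vitamin D. 6.1: withhold vitamin D/placebo | Appendix 5, four rows: withdraw from the study |
| Baseline calcium above 1.32 mmol/L | 3.2.2, Appendix 1 item 14, Appendix 6: ineligible | 3.3.2 and Appendix 15 step 8: vitamin D/placebo removed |
| Order at enrolment | Section 7: eligibility check before the envelope | 3.3.2 describes the envelope, then the calcium; Appendix 15 draws blood after enrolment |

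The 1.32 mmol/L threshold is the same in 3.2.2, Appendix 6 and Appendix 15, so the baseline conflict is about the action. The order in 3.3.2 is implied by its paragraphs and not stated. The constipation row of Appendix 5 also calls for a calcium test, but its hypercalcaemia cell is empty, so four rows is the right count. Asymptomatic cases are outside the on-treatment conflict.

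**2. How many participants**

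The protocol calls the risk of symptomatic hypercalcaemia very low and gives no rate. Assume 1% to 5% on vitamin D and none on placebo, the most one-sided case. The rate also depends on the definition: Appendix 5 counts symptoms with calcium above 1.32 mmol/L, and the grading section of Appendix 6 requires above 1.5.

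- Vitamin D recipients: 2 × 111 = 222.
- Withdrawn: 222 × 0.01 = 2.2 to 222 × 0.05 = 11.1.
- All of these, if found at weeks 2 to 4, could miss the full 2-month composite.
- Week 4 blood and week 4 culture share a visit, so only cases found earlier miss the culture. Assuming half: 1.1 to 5.6.

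**3. Size of the treatment effect for comparison**

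Section 5.1 takes single-treatment proportions from 60% to 40% with an interaction coefficient of 0.5, and gives no scale for it. Three readings:

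| Reading | Combined cell | Vitamin D margin p | Other margin | Effect |
|---|---|---|---|---|
| Additive, half of one effect lost | 30.0% | 35.0% | 50.0% | 15.0 points |
| Log-odds, half of one effect lost | 30.8% | 35.4% | 50.0% | 14.6 points |
| Log-odds, +0.5 added | 32.8% | 36.4% | 50.0% | 13.6 points |

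**4. Largest shift in the vitamin D culture-positive proportion**

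This is for a complete-case analysis with a fraction f lost. If all lost patients were positive, the shift is f(1−p)/(1−f), which flatters vitamin D. If all were negative, it is fp/(1−f), which works against it.

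| f lost before culture | All positive (p = 0.35) | All negative (p = 0.350 to 0.364) |
|---|---|---|
| 0.005 (half of 1%) | 0.33 points | 0.18 points |
| 0.01 | 0.66 | 0.35 to 0.37 |
| 0.025 (half of 5%) | 1.67 | 0.90 to 0.93 |
| 0.05 | 3.42 | 1.84 to 1.92 |

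**5. Power**

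This starts from the stated 82%, which is taken as given: z = 1.960 + 0.915 = 2.875, with 222 × 0.9 = 199.8 evaluable per margin. Let every case be lost before the culture, in addition to the 10% allowance, and scale z by √[(2/199.8)/(1/n + 1/199.8)].

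- f = 0.01: n = 197.8, z = 2.868, power 81.8%.
- f = 0.05: n = 189.8, z = 2.838, power 81.0%.

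**The case against.** The best defence is that the main text is clear and the consequence is speculative.

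- **The cross-reference is narrow.** In 3.3.3.4, Appendix 5 is cited for finding the cause and for reintroducing arginine. The hypercalcaemia sentence gives its own action. This is true, but the doctor is still sent to the table that holds the contrary instruction.
- **Withdrawal is not said to end data collection.** Section 3.3.1 concerns patients who choose to leave, no text drops withdrawn patients from the analysis, and 5.2 points towards keeping them. This stands: loss of outcomes is likely but not stated. Reading the phrase as shorthand for stopping the drug is difficult, because elsewhere the same table names arginine as the drug to stop.
- **Part of the composite has a routine source.** Note 2 to the follow-up table lists weight and symptoms as normal practice. This also stands. FEV1 and culture remain study-only.
- **The Appendix 6 flow chart is not visible.** It may say what staff should do on treatment. Whatever it says, 3.3.3.4 and Appendix 5 still differ.
- **The size is small and the rates are assumed.** Agreed. The 10% loss allowance might already cover these withdrawals, so the power figures lean pessimistic.
- **The baseline part is editorial.** Three places agree on ineligibility and Section 7 already puts the check first. It has no effect on the estimate, but the site instruction that staff would follow on the day says something else.

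**Conclusion.** Both contradictions hold on the current wording. The on-treatment one should be fixed because it could remove participants for a suspected effect of one randomised treatment, contrary to the intention-to-treat aim. Under the assumed 1% to 5% rate with none on placebo, 2 to 11 patients would be withdrawn. With half of them found before week 4, the culture proportion shifts by at most 0.3 to 1.7 points (all lost patients positive) or 0.2 to 0.9 points (all negative). If every case is found before week 4, the shifts are 0.7 to 3.4 and 0.4 to 1.9 points. Power loss is one percentage point or less. At about 1%, closest to what the protocol expects, the bias is negligible. The baseline conflict affects eligibility and the count of randomised patients, not the treatment estimate.

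**What to change.** 1. In the four Appendix 5 rows, replace withdrawal from the study with: stop vitamin D/placebo; the participant stays in follow-up, with all outcomes collected and analysed as randomised. Check that the Appendix 6 flow chart agrees.
2. In 3.3.2 and Appendix 15, require the i-STAT calcium result before the envelope is opened.
3. In 3.3.2, delete the record of exclusion from the vitamin D/placebo component.
4. Limit Appendix 15 step 8 to follow-up visits.

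The cost is wording only. The i-STAT result is already read the same day before any medication is given, so the envelope is opened slightly later in the same visit.

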3.3.3 Study Medications

3.3.3.1 Medication administration

At enrolment, patients will be randomly assigned to one of three groups:

- 1) Group 1: supplementary **L-arginine** 6g daily for eight weeks plus **placebo vitamin D**₃ once every four weeks for two doses (0 and 4 weeks);
- Group 2: supplementary L-arginine 6g daily for eight weeks plus vitamin D₃ (cholecalciferol) 50 000 IU (1250mcg) once every four weeks for two doses (0 and 4 weeks);
- Group 3: placebo L-arginine daily for eight weeks plus vitamin D₃ (cholecalciferol) 50 000 IU (1250mcg) once every four weeks for two doses (0 and 4 weeks);
- Group 4: placebo L-arginine daily for eight weeks plus placebo vitamin D₃ every four weeks for two doses (0 and 4 weeks);

Study drugs will be administered separately from the pre-packaged TB medications, provided in standard Indonesian NTP 'Combipacks' (fixed dose combination therapy for TB).

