5 STATISTICAL ANALYSES

5.1 Sample size

Sample size has been calculated using the graphical method for 2x2 factorial designs informed by the Fleiss equation, described by Byth and Gebski (71). Making a conservative assumption of sub-additive interaction between the 2 interventions (interaction coefficient of 0.5), then at a level of significance of 5%, a sample size of 444 (111 participants in each arm) will provide 82% power to demonstrate that each treatment results in a 20% reduction in the proportion culture positive at one month (from 60% to 40%), assuming loss to follow up of 10%. As there have been no trials of co-administration of vitamin D and L-arginine, the characteristics of potential immunological interactions can be extrapolated only from in vitro macrophage studies, in which findings conflict: vitamin D was found to inhibit iNOS expression in one study(44); yet upregulate NOS2A in another (68); the latter study also found the suppressive effect of vitamin D on MTB replication to be partially impaired if NO formation was inhibited. Including a sub-additive interaction term in the sample size calculation provides a margin a caution; if there is minimal or no interaction between the two interventions, our power will be greater. A factorial design rather than a three-arm study allows us to investigate whether if is safe and effective to co-administer the two interventions. Acknowledging the possibility of statistical interaction between the terms, we have an *a priori* plan to analyse primary and secondary outcomes according to subgroups receiving single interventions as well as according to the overall factorial model (71).

Mean time to culture negativity in mostly drug sensitive TB is 32 days (New York) (72) -57 days (Turkey) (73). Based on bacillary burden and extent of cavitatory disease, we estimate a minimum of 60% of Timika patients will be culture positive at 1 month. Our power will be increased if this proportion is higher. This sample size will also be powered to detect a 9% absolute difference in the mean improvement in percent predicted FEV1, a component of the composite endpoint, at 6 months. Mean baseline percent predicted FEV1 in Timika is 63.6% predicted (SD 22) rising to 77.9% predicted (SD 23) at 6 months. Each month, at least 25 eligible smear positive pulmonary TB patients are diagnosed and treated at the Timika study site. If 90% agree to be enrolled, recruitment will take <2yrs to complete.

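### Appendix 5 lists urticarial rash as a possible arginine reaction, but its management row points away from arginine, stops all TB drugs and gives no step for arginine/placebo

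*Protocol*

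**What the plan says.** Appendix 5 has two parts that bear on this event. The first lists potential effects of each study drug; under arginine its sixth and last item is "Urticarial skin rash". The second is a table of side effects, giving for each the most probable study drug, the most probable TB drug, the tests and the management. Its row for urticarial rash, among the major effects, enters neither study drug and names streptomycin as the TB drug. The management is "Stop all TB drugs. When rash resolved, restart in following order: H, R, Z, E, S S being used i.e. MDRTB" (the end of that cell is garbled in the text as read, which is not a fault of the plan).

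Four other places matter:

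- Section 6.2 on the standard regimen: "This comprises daily weight-adjusted doses of Rifampicin (R), Isoniazid (H), Pyrazinamide (Z) and Ethambutol (E". Streptomycin is not part of it.
- Section 3.3.3.1: "Study drugs will be administered separately from the pre-packaged TB medications". The arginine groups receive "supplementary L-arginine 6g daily for eight weeks", and the other groups a matching daily placebo.
- Section 3.3.3.4: the treating doctor decides which study or TB drug is the likely cause, "according to the strategy outlined in Appendix 5". Then: "If symptoms are determined to be due to arginine, this will be immediately ceased, and reintroduced at a lower dose".
- Appendix 6: a list of recognised effects that do not count as unexpected. It repeats the other five arginine items from Appendix 5 and omits urticarial rash.

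**The concern.** The table is the working instruction for a clinician facing a rash, and section 9.5 also directs staff to Appendix 5 for presumed TB drug reactions. Followed literally, the urticarial row withdraws all TB treatment and leaves in place a blinded product that the same appendix names as a possible cause.

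Two things are at stake. First, TB drugs restart only once the rash has gone. If arginine is the cause and is continued, resolution may be slower and the gap in treatment longer; the row sets no limit on that gap. Second, without an interruption of arginine there is no information on whether the rash improves off the drug. The causality scale in Appendix 6 uses that information for a probable rating and requires it for a definite one. Safety is the first-listed secondary outcome.

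**Working it through.** No figure in the plan needs to be reproduced; the check compares the texts and follows the instruction through.

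**Step 1: what Appendix 5 says about the event.**

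| Place | Study drug | TB drug | Action on TB drugs | Action on arginine/placebo |
|---|---|---|---|---|
| List of potential effects | Arginine | not applicable | none stated | none stated |
| Management row | Neither | Streptomycin | Stop all, restart in sequence after resolution | none stated |

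**Step 2: does the row identify a drug the participant is taking?** Section 3.3.3.4 has the doctor choose among two study drugs and four TB drugs. Section 6.2 gives the four as R, H, Z and E. The row rules neither study drug likely and names a fifth TB drug. For a participant on standard therapy, its attribution columns therefore point to nothing being taken. The action column does cover the first-line drugs, since all are stopped and reintroduced in order. Arginine/placebo is the component left out.

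**Step 3: does stopping TB drugs stop arginine by default?** No. Under section 3.3.3.1 study drugs are given apart from the TB packs, so an instruction about TB drugs does not reach them. The overlap is possible during the eight weeks of arginine/placebo dosing.

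**Step 4: does another rule supply the step?**

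- The stop rule in section 3.3.3.4 takes effect only once symptoms have been attributed to arginine, and that attribution is made by way of Appendix 5. The list there supports attribution; the row does not.
- The arginine footnotes to the table deal with gastrointestinal upset only.
- The table does carry a step to cease arginine in its row for severe anorexia, nausea and abdominal pain, so a study-drug action was within its scope.
- The row for non-urticarial rash also enters neither study drug, but that rash is not listed under arginine. Only the urticarial row conflicts with the list.

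**Step 5: do the two appendices agree?** Appendix 5 lists six arginine effects and Appendix 6 repeats five. The missing one is urticarial rash, so the appendices differ on whether it is expected.

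**Step 6: who is exposed.** Section 5.1 plans "a sample size of 444 (111 participants in each arm"). Two of the four arms contain active arginine: 2 × 111 = 222. The other 222 take its placebo. Because treatment is blinded, the missing step applies to all 444. This counts people taking the product. The documents give no rate of urticaria, so the number affected cannot be calculated.

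**The case against.** The strongest reply is that the two parts of Appendix 5 can both be true. The list concerns potential effects and the table column concerns the most likely drug; a possible cause need not be the most likely one. This stands. A reader might infer a flat contradiction, but the text supports something narrower: a row that leaves out a step for a listed suspect.

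Second, the route to stopping arginine is not closed. Section 3.3.3.4 leaves the judgement to the treating doctor, Appendix 5 includes the list as well as the table, and all potential events go at once to the treating doctor and local investigators (section 9.5). The Appendix 6 event form has codes for reducing, interrupting or discontinuing the study drug. Participants also attend daily in the intensive phase (section 3.3.2). A reader might infer that the protocol requires arginine to continue through a rash; it does not. But the outcome then depends on the doctor looking past the row that deals with the event, and the row steers away from arginine.

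Third, the list entry may be the stray one. Section 6.1 describes only gastrointestinal effects of arginine, Appendix 6 omits urticaria, and the row excludes both study drugs. The documents do not settle this. Even so, while the entry stands, holding the drug when all TB therapy has been stopped is the cautious course.

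**Conclusion.** The point holds as a gap in a safety instruction. Appendix 5 lists urticarial rash under arginine, its row for that event points elsewhere and stops all TB drugs, and nothing in the row deals with arginine/placebo. Section 3.3.3.4 allows a doctor to close the gap but does not do so reliably, because attribution runs back through Appendix 5. Appendix 6 is also out of step.

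In size it is probably small: no event rate is given, and harm requires a rash during the eight weeks of dosing, a doctor who follows the row alone, and arginine as the cause. It merits correction because the consequence for that participant is untreated TB while taking a suspect drug, and because the correction is cheap.

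Two stronger readings are not supported. A reader might infer an effect on culture status at one month; with no event rate, the documents give no basis for one. A reader might also infer that naming streptomycin leaves the first-line drugs unmanaged; the action column stops and restarts them all.

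**What to change.** - In the urticarial-rash row of the Appendix 5 table, enter arginine/placebo as a possible responsible study drug. Add a step to hold it whenever the TB drugs are stopped for this event, without unblinding, as the table's footnotes already provide for other events.
- Leave rechallenge with arginine/placebo to the investigators. Since everything would be stopped together, resolution alone will not identify the cause, so the order of any reintroduction should be recorded.
- Add urticarial rash to the Appendix 6 list of recognised effects, so that the two appendices agree on expectedness.

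The cost is one table row, one list item and a short staff briefing. Design, sample size, randomisation and the layout of the reporting forms are unaffected.
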